4.3 Alternatives

The patient may elect not to participate as an alternative to this study. They will continue to receive their normal care. During informed consent, we will describe our behavioral interventions, study procedures and questionnaires. We will inform our participants about potential risks despite their being minimal. We anticipate that a small proportion of our participants might potentially experience mild discomfort implementing BBT-I procedures (They might experience daytime fatigue and/or sleepiness, and/or memory and concentration difficulties). We will also inform them of the limits in confidentiality, because the intervention may take place in an open area in the ITA if absolutely necessary. We do not have an alternative treatment.

5. INVESTIGATIONAL PROCEDURE INFORMATION

5.1 Investigational Procedure

BBT-I Intervention Group: 90 BC patients will be randomized to receive the BBT-I. BBT-I includes both stimulus control and sleep scheduling, however it has been modified from CBT-I to make it more suitable for cancer patients undergoing chemotherapy with recently developed sleep problems. The main intervention component is one face-to-face 60-minute session with a trained staff member during which time an individually tailored “sleep prescription” is developed. There will also be four 15-minute phone calls and a second 60-minute face-to-face “booster” session. The second face-to-face session will ideally occur during the third or fourth week depending on the patient’s chemotherapy regimen.

BBT-I is a novel intervention that applies innovative cancer-specific chronorehabilitation techniques to effectively treat acute insomnia among patients receiving chemotherapy in the infusion clinic. It is comprised of the following four components: 1) **chronorehabilitation education** (e.g., information on the contribution of circadian disruption to insomnia in the context of cancer and cancer treatment, a review of the cancer-specific behavioral model of insomnia, and discussion regarding how insomnia and fatigue may co-occur and interact.); 2) **light and stimulus control** (e.g., decrease light exposure at night and increase light exposure during the day, do not go to bed until sleepy, and get out of bed if not sleeping); 3) **encouragement of physical activity and discouragement of napping** (e.g., increase exercise and limit naps to 2 per day and no longer than 45 minutes); and 4) **sleep compression** (e.g. increasing motivation to regulate sleep and wake cycles, and go to bed later by at least 15 minutes if sleep efficiency is less than 85%). Patients are told that on their sick days (e.g., days post chemotherapy) they can nap and sleep as much as they need to. In our pilot, we found that patients successfully moderated their sleep prescription on the days when they were not feeling well.

Healthy Eating Education Learning (HEAL) control group: 90 BC patients will be randomized to receive HEAL. HEAL will control for attention and provide a behavioral “placebo.” This control condition will consist of 2 face-to-face sessions and 4 phone calls. The content of the intervention is provided by the NCI: PDQ® Nutrition in Cancer Care. The topics will include nutritional implications of chemotherapy, nutrition screening and assessment, and nutritional suggestions for symptom management (e.g., nausea). To improve the credibility of HEAL

Behavioral Intervention for Insomnia in Cancer

intervention for sleep; the therapists will discuss the connection between healthy eating and good sleep. We expect this to be an aspect of intervention that should bolster the credibility of the control condition as there are sound reasons to think that nutrition could have some effect on insomnia. Nevertheless, we anticipate the effects of HEAL on insomnia would be weak given the evidence behind behaviors that influence sleep which are not targeted by HEAL. In addition, the healthy eating education control has successfully been used as an attention control group for sleep intervention during chemotherapy.^{52,59}

For clinicaltrials.gov and Stanford Clinical Trials Directory compliance

Intervention Description

Women diagnosed with breast cancer receiving chemotherapy will be randomized to either Brief Behavioral Therapy for Insomnia (BBT-I) or Healthy Eating Education Learning (HEAL) control group. BBT-I is a novel intervention that combines chronorehabilitation and cognitive behavioral therapy for insomnia (CBT-I) techniques that are specifically adapted for women diagnosed with breast cancer who are undergoing treatment. Patients randomized to BBT-I will receive 2 face-to-face sessions and 4 phone calls. The control group is patterned after the control group used in a large RCT^{52,53}. HEAL will control for the non-specific components of time, attention, and health education that are not specifically related to sleep management. The control treatment will involve 2 face-to-face sessions and 4 phone calls exactly like BBT-I.

5.2 Availability

Personnel who are trained in the BBT-I and HEAL interventions and are supervised by a clinical psychologist will conduct the sessions with each participant.

5.3 Agent Ordering

N/A; There is no drug utilized in this study.

5.4 Agent Accountability

N/A; There is no drug utilized in this study.

6. DOSE MODIFICATIONS

Half of the participants will be randomized to BBT-I and the other half will be randomized to HEAL. Both groups will receive 6 sessions. There will be no modification in the number of sessions received.

7. ADVERSE EVENTS AND REPORTING PROCEDURES

7.1 Potential Adverse Events

BBT-I may result in temporary increases in daytime fatigue and/or sleepiness, and/or memory and concentration difficulties. Blood drawing may cause pain and bruising at the site where the blood is taken, and sometimes, it causes people to feel light-headed or even to faint. Rarely people might get an infection at the site of the needle stick. Heart rate monitor electrodes and the gel used to attach them may cause a skin reaction.

7.2 Adverse Event Reporting

Adverse events will be graded according to CTCAE v4.03. Both Serious and Non-Serious Adverse Events will be clearly noted in source documentation and listed on study specific Case Report Forms (CRFs). The Protocol Director (PD) or designee will assess each Adverse Event (AE) to determine whether it is unexpected according to the Informed Consent, Protocol Document, or Investigator's Brochure, and related to the investigation. All Serious Adverse Events (SAEs) will be tracked until resolution, or until 30 after the last dose of the study treatment.

SAEs CTCAE Grade 3 and above, and all subsequent follow-up reports will be reported to the Stanford Cancer Institute Data and Safety Monitoring Committee (DSMC) using the study specific CRF regardless of the event's relatedness to the investigation. Following review by the DSMC, events meeting the IRB definition of 'Unanticipated Problem' will be reported to the IRB using eProtocol within 10 working days of DSMC review, or within 5 working days for deaths or life-threatening experiences.

8. CORRELATIVE/SPECIAL STUDIES

8.1 Laboratory Correlative Studies

8.1.1 (Inflammation, Telomeres and Circadian Disruption and Sleep – Laboratory Correlative Study #1)

8.1.1.1 Blood collection will be done to estimate hematocrit, hemoglobin, and cytokines (and telomere length. Patients will collect saliva 5 times a day over a course of two days (when they first wake up, 30 minutes after waking, 12PM, 5PM and before bedtime). Saliva will be stored in the patients' refrigerator over the course of two days and then returned at assessment to be stored at the Department of Psychiatry.

8.1.1.2 Blood draws will be conducted at either Stanford Hospital Drop-In or CTRU labs. Ideally, the blood samples will be drawn first thing in the morning after patients have fasted since midnight. A minimum of 4 hours is required if the patient is unable to come for a blood draw the first thing in the morning. A one- hour resting period is required. However, if an afternoon fasting sample is the only time that a patient is available, then we will collect at that time point. Whether the collection time is in the morning or afternoon, the collection time will remain consistent within each subject once the baseline is collected. We will keep records of the patient's last meal, length of resting period and time of blood draw.

8.1.1.3 Samples will be processed at Stanford Labs where they will be spun and aliquoted, if shipment to another site is warranted, the samples will be shipped de-identified via FedEx and following bloodborne pathogen protocol for shipping. All of the study staff arranging shipment will be certified and trained in handling of bloodborne pathogens for shipment.

8.1.1.4 Blood analyses will be conducted at HIMC and saliva analyses will be conducted at Stanford Labs.

8.1.1.5 Blood collection tubes and saliva salivettes will be bar coded with study number rather than PHI. Each Tube will be labeled with the following information: MOSAIC, Subject#,

Behavioral Intervention for Insomnia in Cancer
Date&Time Collected.

Behavioral Intervention for Insomnia in Cancer

9. STUDY CALENDAR

	Baseline	Post Intervention	6 Month Follow-up	12 Month Follow-up
On Study Data (Demographic and clinical data)	X			
Clinical Record Information (Clinical data)	X			
Demographic Questionnaire/Medication	X			
Insomnia Severity Index (ISI)	X	X	X	X
Brief Fatigue Inventory (BFI)	X	X	X	X
Hopkins Verbal Learning Test (HVLT)	X	X	X	X
Clinical Assessment of Depression (CAD)	X	X	X	X
Mobile Cognitive Assessment Battery (MCAB)	X	X	X	X
Comprehensive Trail Making Test (CTMT)	X	X	X	X
Controlled Oral Word Association Test (COWAT)	X	X	X	X
Heart Rate Variability	X	X	X	X
Blood Draw	X	X	X	X
Actigraphy	1 week	1 week	1 week	1 week
Saliva Collection	X	X	X	X
Sleep Behavioral Self Rating Scale (SBSRS)	X	X	X	X
Pittsburgh Sleep Quality inventory (PSQI)	X	X	X	X
Dysfunctional Beliefs about Sleep (DBAS)	X	X	X	X
Difficulties in Emotion Regulation Symptoms (DERS)	X	X	X	X
European Organisation for Research and Treatment of Cancer (EORTC) Quality-of-Life-Questionnaire-C30	X	X	X	X
Godin Leisure Time Exercise Questionnaire (GLTEQ)	X	X	X	X
Reduced Home Ostberg Morningness Eveningness Questionnaire (rMEQ)	X	X	X	X
Nutrition Knowledge Questionnaire (NKQ)	X	X		
Sleep Diaries	1 week	1 week	1 week	1 week
Daily Diaries	1 week	1 week	1 week	1 week
BBT-I/HEAL Checklists		6 times during intervention		
Feedback	X	X		

10. MEASUREMENTS

For clinicaltrials.gov and Stanford Clinical Trials Directory compliance

Primary Outcome Measure Insomnia.

- **Title:** Insomnia Severity Index
- **Time Frame:** Pre, post intervention and at 6 and 12 months follow-ups.
- **Safety Issue:** No

Note: Each outcome measure listed within the protocol will necessitate legally required results reporting to clinicaltrials.gov within one year after the completion of the primary outcome measure.

10.1 Primary and Secondary Outcome measures

Primary Outcome Measure of Insomnia. The effects of the BBT-I intervention on insomnia will be measured by the Insomnia Severity Index (ISI), which is a well-validated self-report measure of sleep.⁶⁰⁻⁶² The primary outcome will be the change from baseline to 6-month follow-up. A change score of -6 is considered a minimally clinically significant difference for the ISI.⁶⁰⁻⁶² The measure consists of seven questions on a 5-point Likert Scale with a total score ranging from 0-28. Reliability and validity of this measure have been established.⁶⁰⁻⁶² The ISI is the primary outcome measure for the study.

Secondary Outcome: Fatigue will be assessed with the revised Brief Fatigue Inventory (BFI), a 9-item, patient-report instrument that we have used in previous studies with established reliability and validity.⁶³ The BFI allows for rapid assessment of fatigue level in BC patients and identifies those with severe fatigue.

Secondary Outcome: Cognitive Difficulties will be assessed using a cognitive battery of self-rating questionnaires including the Clinical Assessment of Depression (CAD), as well as the Self-Rating subtest of the Mobile Cognitive Assessment Battery (MCAB). CAD has been shown to discriminate between chemotherapy-treated BC patients and controls and also correlate significantly with neurobiologic and immunologic deficits in BC.⁶⁴⁻⁶⁶ We will additionally administer a battery of neuropsychological assessments, including the Comprehensive Trail Making Test (CTMT), Hopkins Verbal Learning Test Revised (HVLT-R), Controlled Oral Word Association Test (COWAT), and the Mobile Cognitive Assessment Battery. The CTMT is an objective, standardized neuropsychological measure of executive function (switching/inhibition), attention, sequencing and processing speed.⁶⁷ The International Cognition and Cancer Task Force recommends the CTMT for harmonizing studies of cognitive function in cancer populations.⁶⁸ The CTMT requires 5 to 12 minutes to administer and is normed for individuals aged 8 to 74 years. It has a reliability coefficient of 0.90 or higher for all ages.⁶⁹⁻⁷¹ The COWAT is a verbal fluency task that assesses complex cognition. This test has been used in previous studies with breast cancer patients and has shown strong differences between cancer patients and controls.⁷² The COWAT takes 4-5 minutes to administer. The HVLT-R is a list memory exercise that measures verbal learning and memory, as well as delayed recall. The test requires a total time of ten minutes with a 20-25 minute period between delayed recall and recognition. HVLT-R has been used in many clinical populations, including breast cancer.^{73,74} The MCAB was specifically designed to be more sensitive at capturing cognitive impairments in the clinical

Behavioral Intervention for Insomnia in Cancer

setting. The MCAB is comprised of three neuropsychological tests (in addition to a self-report measure) measuring cognitive flexibility, accuracy, processing speed, working memory and multitasking. The battery has been shown to be clinically significant in breast cancer populations and shows increased sensitivity compared to traditional tests.⁷⁵ This battery is delivered through the MCAB iPad application and takes approximately 15 minutes to complete.

Physiological Mediators Heart Rate Variability (HRV) will be calculated with the ambulatory monitoring heart-rate device Firstbeat® that measures RR intervals with a rating sample of 1ms. The device utilizes a valid and reliable method for sampling RR intervals and provides software to analyze the raw data.⁷⁶⁻⁷⁸ We will calculate time and frequency domain measures of HRV: SDNN, (the standard deviation of all normal RR intervals measured between consecutive sinus beats) and RMSSD (the root mean square of successive differences between adjacent normal R-R intervals).^{76,79} In addition, we will measure frequency domain measures, natural log of high frequency (HF, total spectrum power of all NN intervals between 0.15 to 0.4Hz) for vagal tone/RSA and natural log of low frequency (LF, total spectrum power of all NN intervals between 0.04 to 0.15Hz) and LF/HF ratio. Given our preliminary data in BC patients, we will use RSA as a primary HRV outcome. Heart rate variability data will not be collected from a participant if she has an implanted device for heart failure (e.g., pacemaker, defibrillator, left ventricular assist device, etc.).

Circadian Rhythm will be assessed using actigraphy and salivary cortisol at each of the 4 assessment points (sleep diaries are used for cross-checking the going to sleep and waking up times). A two-oscillator cosinor model (12 and 24 hours) will be calculated using nonlinear regression methods on the log (activity counts). This model was found to fit the data for cancer survivors⁸⁰ better than a single-oscillator model. Mesor (overall), Amplitude, and Acrophase for the 12- and 24-hour cycles will be calculated. In addition, we will collect salivary cortisol per modified McArthur protocol⁸¹ for 2 days at wake, wake +30, 12PM, 5PM and before bedtime (baseline, 6-, 30-, and 58-weeks). Saliva samples will be refrigerated after collection and stored at -70 °C within a couple of days of collection. Samples will be assayed using a luminescence immunoassay (Immuno-Biological Laboratories Inc, Germany) at Stanford Labs.

Reduced Horne Ostberg Morning Evening Questionnaire (rMEQ) will determine the chronotype of the participant to help assess activity of various physical functions. This questionnaire is a shortened version of the Horne-Ostberg Morning Eveningness Questionnaire.⁸² It is a seven-item questionnaire that asks various questions of daily choices regarding sleep and other activities.

Behavioral Mediators and Moderators Maladaptive sleep behaviors will be assessed with the Sleep Behavioral Self- Rating Scale (SBSRS),⁸³ the Pittsburgh Sleep Quality Inventory (PSQI)⁸⁴ sleep diaries and actigraphy. The SBSRS is a validated measure that helps understand patient's adherence to stimulus control. Sleep continuity will be assessed subjectively using Daily Sleep/Wake Diaries and via PSQI. These sleep continuity measures will be used in the meditational analyses and will provide important supplemental data on frequency, severity, and type of sleep problems encountered by patients, as well as contributing factors.

Participants will also have their sleep-wake exposure monitored through the use of a wrist-worn actigraphy-based data logger (Actiwatch-64, MiniMitter, Bend OR). We will set the Actiwatch to record activity counts every 1 minute; at this setting it can record up to 45 days worth of data before the internal memory is full. Actigraphy data will be analyzed using Actiware® software (v.5.04.003, MiniMitter, Bend OR). The program uses a validated sleep algorithm to provide an

Behavioral Intervention for Insomnia in Cancer

assessment of sleep by delineating the “in bed” and “out of bed” portions of the day. The actigraphy, in conjunction with the sleep/wake diaries, can be used to approximate the timing of both daytime and nighttime sleep and provide information on maladaptive sleep behaviors (i.e., increased time in bed, bedtime and rise time variability).⁸⁵ While daily sleep diaries are a method commonly used to examine patterns of sleep and wakefulness, we will internally validate the at-home monitoring by comparing actigraphy data collected during baseline and follow-ups to the daily diaries. This measurement strategy allows for an assessment of sleep problems (WASO), that is free from either subjective or observer bias and requires minimal subject compliance, allows for the detection of periods of wakefulness as brief as 30 seconds in duration, and allows for the continuous assessment of sleep and wakefulness for periods of up to 30 days.

The dysfunctional beliefs about sleep will be measured utilizing the Dysfunctional Beliefs and Attitudes about Sleep Scale,⁸⁶ a self-report measure that was designed to examine changes in erroneous sleep beliefs and attitudes. Potential moderators will be assessed using age, baseline anxiety and depression (Clinical Assessment of Depression), hot flashes (daily diary), caregiver status (questionnaire), as well as emotional regulation (Difficulties in Emotion Regulation Symptoms). The Nutrition Knowledge Questionnaire (NKQ) will also be used to control for attention.

The Difficulties in Emotion Regulation Scale (DERS)⁸⁷ will be used to determine emotion regulation. The DERS is a brief, 36-item, self-report questionnaire devised to assess several aspects of emotion dysregulation. The measure yields a total score as well as scores on six scales produced through factor analysis: Nonacceptance of emotional responses (NONACCEPTANCE), difficulties engaging in goal directed behavior (GOALS), impulse control difficulties (IMPULSE), lack of emotional awareness (AWARENESS), limited access to emotion regulation strategies (STRATEGIES), and lack of emotional clarity (CLARITY). This measure has been found to have high internal consistency, good test–retest reliability, and adequate construct and predictive validity.

Other variables. We will extract the following medical variables from the patients’ medical records: disease stage, chemotherapy type (e.g., doxorubicin), prior treatment (e.g., surgery), and receptor status. We will record the treatment that the patient is on during each assessment point to account for differences that might be associated with their particular treatment regimen. We will also determine exercise and physical activity through the Godin Leisure Time Exercise Questionnaire (GLTEQ). The GLTEQ is a 4-item test that asks the frequency of strenuous, moderate and mild exercise. It has been validated to examine changes of behavior in activity.⁸⁸ The NKQ will be given to enhance the validity of the control intervention. It is a 15-item questionnaire that measures competency of nutrition.

Expectancy/Feedback will be obtained by 2 checklists assessing the usefulness and acceptability of the experimental interventions and intervention outcome expectancy. Participants will complete the expectancy checklist at the end of their first face-to face session and feedback questionnaire at post-intervention to assess whether they found our interventions helpful for their symptoms. For these baseline variables that are not considered as potential moderators, given our strong design based on random assignment to treatment and control groups, it is reasonable to assume that they will be balanced between the intervention and control groups (i.e., no need to worry about controlling for them). Nonetheless, we will test sensitivity of our results to presence/absence of these potential baseline covariates, especially those that differ between groups due to natural experimental error.

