INVESTIGATIONAL PRODUCT OR PROCEDURE	Brief Behavioral Therapy for Insomnia (BBT-I) H ea l thy E ating E duc a tion L earning (HEAL)
PRIMARY OBJECTIVE(S)	The purpose of this study is to test the efficacy of brief behavioral therapy versus control condition that accounts for time and attention (nutrition education) in the treatment of insomnia in humans.
SECONDARY OBJECTIVE(S)	To assess the impact of different biomarkers on sleep disruption and other patient reported outcomes
TREATMENT SUMMARY	This research is designed to determine the efficacy of the BBT-I in comparison with the attention-matched behavioral control in reducing insomnia, fatigue, and cognitive difficulties in breast cancer patients. In addition, this study will examine the potential involvement of moderators (age, depression, anxiety, and hot flashes), specific behavioral mechanisms (maladaptive sleep behaviors, dysfunctional beliefs and attitudes), and physiological mechanisms (dysregulated circadian rhythms, disrupted wake-sleep cycles, and autonomic tone) as potential mediators of intervention-related changes in insomnia and the secondary outcomes of fatigue and cognitive difficulties. To address these aims, 180 breast cancer patients with acute insomnia during chemotherapy treatment will be recruited and randomized to receive either BBT-I or a behavioral control focused on healthy eating education. Each intervention condition will consist of 2 face-to-face sessions + 4 phone calls, delivered over a period of six weeks. Assessments will include sleep diary, questionnaires, neuropsychological testing, actigraphy, heart rate variability measurement, and salivary cortisol collection at baseline, post-intervention, and 6- and 12 months follow ups. By offering this intervention during

Behavioral Intervention for Insomnia in Cancer

	chemotherapy when patients are just beginning to develop insomnia, we hope to alleviate and avoid the development of chronic insomnia in the survivorship phase.
SAMPLE SIZE	180
STATISTICAL CONSIDERATIONS	The primary endpoint is insomnia. Secondary endpoints include cognitive functioning, fatigue, depression, HRV, cortisol and biomarkers of sleep and stress. The estimated power to detect the group difference in change in ISI is 0.88-0.99 (d=0.4 to 0.6, alpha=.05, two-tailed) with N=180 (90 BBT-I, 90 control).

Behavioral Intervention for Insomnia in Cancer

SCHEMA

LIST OF ABBREVIATIONS AND DEFINITION OF TERMS (Example)

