In our mixed effects analyses, the change in the outcome will be modeled as the key dependent variable predicted by the treatment status. The results of these longitudinal analyses can be easily converted to treatment effect at each assessment point to directly respond to our specific hypotheses. In particular, we are interested in the main effect of treatment (BBT-I vs. Control) at 12-month follow-up (58 week) assessment. The same analysis strategy will be employed for Hypothesis 2, where we will examine the treatment effects on secondary outcomes such as fatigue (measured by BFI) and cognitive difficulties (measured by Cognitive Battery). In Hypothesis 3, we will examine the mediators of treatment effects on insomnia, fatigue, and cognitive difficulties.

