12.5 Secondary Analysis

Aim 2 (Secondary): To evaluate efficacy of the BBT-I in treating cancer-related symptoms such as cancer-related fatigue and cognitive difficulties in breast cancer patients receiving chemotherapy.

Hypothesis 2 (Secondary): BBT-I compared to an attention control group will be associated with greater improvements in fatigue and cognitive difficulties (as measured by the Brief Fatigue Inventory, and our Cognitive Battery that includes neuropsychological testing) from baseline through the 12 month follow up.

Aim 3 (Secondary): To examine potential moderators and mediators of BBT-I intervention effects on insomnia, cognitive difficulties, and fatigue. In particular, we are interested in age, depression and anxiety, emotion regulation and side effects (hot flashes) as potential moderators of the intervention effects as well as evaluating modifiable behavioral and physiological mechanisms as hypothesized mediators.

Hypothesis 3 (Secondary): In women with breast cancer receiving chemotherapy, intervention effects on insomnia, fatigue, and cognitive difficulties will be mediated by select behavioral mechanisms [i.e., maladaptive sleep behaviors (The Sleep Behavior Self-Rating Scale, sleep diaries, actigraphy), dysfunctional beliefs and attitudes (Dysfunctional Beliefs and Attitudes about Sleep) and physiological mechanisms [i.e., dysregulated circadian rhythms (measured by salivary cortisol), disrupted sleep wake cycles (actigraphy), and autonomic tone (RSA)].

As hypothesized mediators, we will carefully examine behavioral (measured by DBAS, SBSRS and sleep diaries) and physiological mechanisms (measured by HRV, salivary cortisol and actigraphy). Examination of moderators will be exploratory. As potential moderators, we will examine age, baseline anxiety and depression, baseline emotion regulation and baseline hot flashes. Among these potential moderators, some will not be qualified as moderators but predict outcome regardless of the intervention assignment status (we will classify these as non-specific predictors of the outcome). For the moderator/mediator investigation, we will apply the McArthur framework.^{98,99} Our analysis strategy in detecting moderators and mediators is mixed effects modeling, where the McArthur approach will be embedded.

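### The depression scale (CAD) sits inside the cognitive-difficulties outcome of Hypothesis 2, so a change in mood could be reported as a cognitive benefit; how easily depends on a scoring rule the plan does not give.

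*Combined protocol and SAP*

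**What the plan says.** Section 10.1, under the secondary outcome of cognitive difficulties, names two self-ratings. It uses "a cognitive battery of self-rating questionnaires including the Clinical Assessment of Depression (CAD") and the self-rating part of the MCAB. It then adds performance tests: CTMT, HVLT-R, COWAT and the MCAB tests.

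Later in section 10.1 the CAD has a different role: "Potential moderators will be assessed using age, baseline anxiety and depression (Clinical Assessment of Depression), hot flashes (daily diary"). Section 12.5 carries these moderators into the analysis: "As potential moderators, we will examine age, baseline anxiety and depression, baseline emotion regulation and baseline hot flashes". Aim 3 covers "potential moderators and mediators of BBT-I intervention effects on insomnia, cognitive difficulties, and fatigue".

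The synopsis separates the two constructs: "Secondary endpoints include cognitive functioning, fatigue, depression, HRV, cortisol and biomarkers of sleep and stress". The study calendar (section 9) names no other instrument as a depression scale.

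Hypothesis 2 identifies its endpoints "as measured by the Brief Fatigue Inventory, and our Cognitive Battery that includes neuropsychological testing", and section 12.4.2 refers to "cognitive difficulties (measured by Cognitive Battery"). Neither place lists the components, gives a composite rule, names a key component or names a CAD subscale.

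**The concern.** The plan treats one instrument as a mood measure in some places and as a cognition measure in another. Section 2.3 supplies the route by which this matters: it describes depression and insomnia as strongly correlated and suggests that treating insomnia might affect depression. A CAD response with no change in cognition is therefore something the plan itself allows for, and under section 10.1 it would fall within cognitive difficulties.

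Nothing later in the plan guards against this. Section 12.6.2 declines to adjust for the multiple secondary outcomes. No success rule is set for the cognitive part of Hypothesis 2. Assessor blinding (sections 3.4 and 12.1.1) does not protect a self-rating when section 2.4 describes the trial as open. At stake is whether a claim of cognitive benefit can be read as one.

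**Working it through.** **The plan's own figure.** There is none for the CAD or for the cognitive battery. The nearest is in section 12.6.2: power 0.84 to 0.91 for the BFI at d = 0.35 to 0.4. A simple two-sided two-sample calculation gives 0.65 and 0.77 with 90 per arm, and 0.53 and 0.64 with 67.5 per arm. The plan used a growth model whose slope variance and covariances are not given, so the BFI figure can be neither reproduced nor refuted. It is not used below.

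**Inputs from the plan.**
- 90 per arm and two-sided alpha 0.05 (section 12.6.2).
- 25% attrition by the 6-month assessment (section 12.6.2): 90 × 0.75 = 67.5, taken as 67 per arm at the low end.
- d = 0.35 to 0.4, the range that section 12.6.2 uses for Hypothesis 2.

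**Assumptions that are not in the documents.**
- The intervention shifts the CAD by that d and shifts every true cognitive measure by 0.
- Components have equal variance and pairwise correlation 0.3.
- For the composite of six, the components are the CAD, MCAB self-rating, CTMT, HVLT-R, COWAT and MCAB tests, with equal weights.

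**Formulas.** For a mean of k standardised components of which only the CAD moves, the apparent effect is d_k = (d/k) / √[(1 + (k − 1) × 0.3)/k]. With λ = d_k × √(n/2), the chance of a significant result is Φ(λ − 1.96) + Φ(−λ − 1.96).

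**Results (low end: d = 0.35, n = 67; high end: d = 0.4, n = 90).**

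| Scoring of the battery | Apparent d | λ | Chance of significance |
|---|---|---|---|
| CAD analysed as its own measure (k = 1) | 0.35 to 0.40 | 2.03 to 2.68 | 53% to 77% |
| Mean of the two self-ratings (k = 2) | 0.22 to 0.25 | 1.26 to 1.66 | 24% to 38% |
| Mean of six components (k = 6) | 0.09 to 0.10 | 0.52 to 0.69 | 8% to 11% |

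Worked low end for k = 6: (0.35/6)/√(2.5/6) = 0.0583/0.6455 = 0.090; λ = 0.090 × √33.5 = 0.52; 0.075 + 0.007 = 0.082.

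**Separate unadjusted tests.** If the six components are each tested at 0.05 and treated as independent, the chance that at least one is significant is 1 − (1 − P_CAD) × 0.95⁵, which is 63% to 82%. The five components other than the CAD would give 1 − 0.95⁵ = 23% on their own with no true effect.

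With the CAD taken out of the cognitive endpoint, an effect on the CAD alone contributes nothing to it.

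**The case against.** The strongest reply is that this is one component of an unadjusted secondary outcome and that the plan has partial safeguards. Hypothesis 2 includes neuropsychological testing. The note in section 10 expects results to be posted for each listed outcome measure, so a change confined to the CAD might be visible as such. Section 12.6.2 puts more emphasis on clinical than on statistical significance for the secondary hypotheses. All of that stands, and it limits the claim to what could happen. It does not remove the CAD from the cognitive outcome.

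Four stronger readings are tempting, and the documents do not support them.

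- *A mood effect is bound to be reported as cognitive benefit.* The battery has no stated scoring, and in an equal-weight six-component composite the carry-over is small.
- *Using the CAD as a moderator is itself an error.* Only "baseline anxiety and depression (Clinical Assessment of Depression") is used, and sections 12.3 and 12.5 call the moderator work exploratory. A baseline score is an ordinary candidate moderator, including when the scale is measured again later. For insomnia and fatigue there is no overlap. The overlap matters only when the moderated outcome is a cognitive battery that contains the CAD, because baseline CAD is then also the baseline of one of its components.
- *The plan's 0.84 is the chance of a spurious cognitive finding.* That figure is power for the BFI. The plan gives no power or reliability for the CAD.
- *The percentages are type I error rates to set against 0.05.* They are the power to detect an assumed real effect on the CAD that would then carry the wrong label. For separate tests, the relevant comparison is the 23% above.

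A further point is fair. Section 10.1 supports the CAD with cited studies that cannot be consulted here. One can say that its text does not state that the CAD measures cognition: it mentions discrimination from controls and correlation with neurobiologic and immunologic deficits. One cannot say that the CAD has no cognitive content.

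**Conclusion.** The concern holds as an inconsistency in how the endpoint is defined. By the plan's own wording the CAD belongs to cognitive difficulties, while elsewhere it is the depression and anxiety measure and depression is a separate endpoint. No section excludes it from the battery or restricts it to a cognitive subscale.

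The consequence ranges from slight to serious, and the missing scoring rule decides which: roughly 8% to 11% for a six-component composite and up to 53% to 77% if the CAD stands alone. These figures rest on an assumed CAD effect of 0.35 to 0.4, no cognitive effect, and an assumed correlation of 0.3 for the composites; the documents support none of these directly. Because the scoring is open, the choice could be made after the data are seen, which is the main reason to settle it beforehand. The primary ISI analysis is unaffected.

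**What to change.** In sections 10.1 and 12.5:

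- Report the CAD as the depression secondary endpoint that the synopsis already lists, and keep its baseline value as the exploratory depression and anxiety moderator.
- Define the Hypothesis 2 cognitive endpoint by CTMT, HVLT-R, COWAT and the MCAB. State how they are scored, and report the performance tests separately from the MCAB self-rating, to which the same worry about mood-driven self-report could apply.
- If a cognitive subscale of the CAD was intended, name it, justify it, and keep it out of the depression moderator score.

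The cost is a protocol wording amendment. Section 11.1 requires IRB approval before it is implemented, and the outcome list used for results reporting (section 10) may need to match. Visits, instruments, sample size and the primary analysis do not change.
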